## 2.5. Outcomes

### Primary Outcome

- **Weight gain over 8 weeks (Specific Aim 1).** Weight will be measured at all follow-up time points and weight gain will be defined as grams per kilogram per day (g/kg/day).

[figure not shown]
### Secondary Outcomes

- **Nutritional recovery by 8 weeks (Specific Aim 2).** Nutritional recovery will be defined as a child having WHZ  $\geq -2$  on two consecutive visits and no acute complication or edema for the past 7 days OR MUAC of  $\geq 125$ mm on 2 consecutive visits and no acute complication or edema for the past 7 days. The criteria chosen to define the recovery will be the same one we used to admit the child into the program.

- **Time to recovery.** Time from enrollment to nutritional recovery (defined above) will be calculated in days by subtracting the date of enrollment from the date of nutritional recovery.
- **Nonresponse at 8 weeks.** Nonresponse will be documented if a child does not meet the criteria for nutritional recovery at 8 weeks.
- **Transfer to inpatient care.** The occurrence, date, and reason for transfer from outpatient to inpatient treatment will be recorded.
- **Mortality by 8 weeks.** Vital status will be assessed at all follow-up time points and mortality will be defined as death during the study period. Date of death will be recorded.
- **Clinical signs of infection.** At all follow-up time points, clinical signs of infection will be recorded, including care-giver reported experience of fever, diarrhea, vomiting, and respiratory infection/cough and clinical diagnoses made at by site personnel
- **Adverse events.** Adverse events will be reported at all follow-up time points (defined in Section 5).
- **HAZ.** Height or length will be measured at all follow-up time points and height-for-age z-scores will be calculated.
- **MUAC.** Mid-upper arm circumference will be measured at all follow-up time points.
- **WAZ.** Weight will be measured at all follow-up time points and weight-for-age z-scores will be calculated.
- **WHZ.** Weight and height, assessed at all follow-up time points, will be used to calculate weight-for-height z-scores.
- **Malaria.** Rapid diagnostic tests for malaria will be conducted at baseline and week 8 to determine malaria infection status.
- **Intestinal microbiome:** Rectal swabs will be collected in a random subset of children at baseline and at week 8.

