#### **Eligibility criteria for individuals**

Eligible individuals are children aged 6-59 months with SAM who present to an eligible enrollment site during the study period and meet all of the following criteria:

*Inclusion criteria (all must be met):*

- Age 6-59 months
- Weight-for-height z-score (WHZ) < -3 SD or mid-upper arm circumference (MUAC) < 115 mm
- No nutritional edema
- Primary residence within catchment area of enrollment site
- Available for full 8-week study
- Has not been admitted to a nutritional program for the treatment of SAM in the 2 preceding weeks
- No antibiotic use in past 7 days
- No clinical complications requiring antibiotic treatment
- No clinical complications requiring inpatient treatment
- No congenital abnormality or chronic debilitating illness that would lead to predictable growth faltering or reduce likelihood of SAM treatment benefit (such as cerebral palsy, Down syndrome, congenital heart disease, cleft lip/palate, etc)
- No allergy to macrolides/azalides
- Sufficient appetite according to a feeding test with ready-to-use therapeutic food (RUTF)
- Appropriate written informed consent from at least one parent or guardian

*Exclusion criteria (any excludes):*

- Age < 6 months or > 59 months
- WHZ  $\geq$  -3 SD or MUAC  $\geq$  115 mm
- Primary residence outside catchment area of enrollment site
- Not available for full 8-week study
- Presence of nutritional edema
- Admission to a nutritional program for the treatment of SAM in the 2 preceding weeks
- Antibiotic use in past 7 days
- Clinical complications requiring antibiotic treatment
- Clinical complications requiring inpatient treatment
- Congenital abnormality or chronic debilitating illness that would lead to predictable growth faltering or reduce likelihood of SAM treatment benefit (such as cerebral palsy, Down syndrome, congenital heart disease, cleft lip/palate, etc)
- Allergy to macrolides/azalides
- Insufficient appetite according to a feeding test with ready-to-use therapeutic food (RUTF)
- Parent or guardian refuses to provide consent

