### 9.2. Statistical Analysis

**Baseline characteristics.** Characteristics of the study population collected at baseline will be summarized using frequencies and percentages for categorical variables and means and standard deviations or medians and inter-quartile ranges for continuous variables. Baseline characteristics will be compared by treatment arm using Fisher's exact test for categorical variables and t-tests or Wilcoxon rank-sum tests for continuous variables.

**Specific Aim 1.** The primary analysis will compare weight gain velocity (g/kg/day) between groups over the 8-week follow-up period,. We will estimate mean differences and 95% confidence intervals for the difference using a linear regression model with an indicator for study group.

$$E[Y | X = x] = \beta_0 + \beta_1 X + e$$

Where:

- $Y$  = weight gain velocity from enrollment to 8 weeks
- $X$  = binary indicator for treatment group ( $X=1$  for azithromycin,  $X=0$  for a short course of oral amoxicillin)
- $\beta_1$  = difference in weight gain velocity between the azithromycin group compared to a short course of oral amoxicillin group

- $e \sim N(0, \sigma^2)$

**Specific Aim 2.** The primary analysis will compare nutritional recovery by 8 weeks from baseline by arm. We will use log-binomial regression for this analysis to estimate the risk ratio. We will use the following model:

$$\log[P(Y = 1|X_1 = x_1)] = \beta_0 + \beta_1 X_1 + e$$

Where:

- $Y$  = binary indicator for nutritional recovery by 8 weeks ( $Y=1$  for recovered,  $Y=0$  for not recovered)
- $X$  = binary indicator for treatment arm ( $X=1$  for azithromycin,  $X=0$  for a short course of oral amoxicillin)
- $e^{\beta_1}$  = relative risk of nutritional recovery in azithromycin arm compared to a short course of oral amoxicillin arm
- $e \sim N(0, \sigma^2)$

If the log-binomial model fails to converge, we will use a modified Poisson model with robust standard errors as an alternative.

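### The recovery rule gives no single target for a child admitted on both WHZ and MUAC, and the Aim 2 and time-to-recovery analyses ignore admission type

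*Combined protocol and SAP*

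**What the plan says.** **Entry.** Section 2.2 of the combined protocol and SAP includes children with "Weight-for-height z-score (WHZ) < -3 SD or mid-upper arm circumference (MUAC) < 115 mm". The exclusion list in the same section, where any one item excludes, has "WHZ $\geq$ -3 SD or MUAC $\geq$ 115 mm".

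**Recovery.** Section 2.5 gives two targets. The first branch begins "Nutritional recovery will be defined as a child having WHZ" and requires a z-score of at least -2 at two consecutive visits. The second is "OR MUAC of $\geq 125$ mm on 2 consecutive visits". Both also require a week free of acute complication and edema. The definition ends: "The criteria chosen to define the recovery will be the same one we used to admit the child into the program".

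**Analysis.** Section 9.2 takes as the Aim 2 outcome a "binary indicator for nutritional recovery by 8 weeks" and says "We will use log-binomial regression for this analysis to estimate the risk ratio". The only explanatory variable is a "binary indicator for treatment arm". Time to recovery is compared with a log-rank test, and no stratification is mentioned. Section 2.3 describes 1:1 allocation without strata. Baseline correction is planned for the secondary anthropometric outcomes only. Baseline WHZ and MUAC otherwise appear only in the missing-data weights.

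**Follow-up.** Sections 2, 2.4 and 3.2 have weekly visits and anthropometry until recovery, then a visit at week 8. Section 6.1 speaks of data collection in weeks 1 to 8 but does not say that weekly anthropometry continues after recovery.

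**The concern.** The linking sentence presumes one admission criterion per child, but the inclusion rule is not an exclusive choice. For a child below both cut-offs, the text supports four readings of recovery: the WHZ target, the MUAC target, either, or both. Two assessors could score identical measurements differently.

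The same definition feeds the Aim 2 endpoint, time to recovery and nonresponse, and it ends weekly measurement. If a dual-criterion child is declared recovered on one target, the later weekly measurements needed to apply another reading may never be taken. The gap therefore cannot be relied on to close at the analysis stage.

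A second, smaller issue concerns children admitted on one criterion. Some must gain at least 1 SD in WHZ (from below -3 to -2) and others at least 10 mm in MUAC (from below 115 to 125 mm). The Aim 2 model and the log-rank test pool these groups without an admission-type term.

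**Working it through.** **1. Side-by-side reading.**

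| Child at entry | Inclusion line | Exclusion line, read literally | Recovery target |
|---|---|---|---|
| WHZ < -3 only | eligible | excluded (MUAC ≥ 115 mm) | WHZ |
| MUAC < 115 mm only | eligible | excluded (WHZ ≥ -3) | MUAC |
| Both | eligible | not excluded | not stated |

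The two lists disagree about the first two rows. If the exclusion line governs, every enrolled child falls in the row with no stated target. If the inclusion line governs, only a share does, and the documents do not give that share.

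Example: a dual-criterion child has WHZ ≥ -2 at weeks 4 and 5, MUAC 114 mm at week 5, and no complication or edema. On the either reading the child has recovered at week 5. On the both reading the child has not, and MUAC still meets the trial's entry cut-off. If weekly visits stop at week 5, only the week 8 visit remains, while the definition needs two consecutive visits.

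**2. The plan's own figure.** Inputs from Section 9.1: 66% against 81%, two-sided alpha 0.05, 270 evaluable (135 per arm). With pooled variance under the null and mean proportion 0.735:

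- Numerator: 0.15·√135 − 1.96·√(2·0.735·0.265) = 1.743 − 1.223 = 0.520
- Denominator: √(0.66·0.34 + 0.81·0.19) = √0.3783 = 0.615
- Power = Φ(0.520/0.615) = Φ(0.845) = 80.1%

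Required n is 135 per arm, and 135/0.90 = 150. The stated size reproduces.

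**3. How far the reading could move the recovery level (illustration).** Assume each target is met by 66% of dual-criterion children, with latent bivariate-normal correlation 0.3 to 0.7. P(either) = 2·0.66 − P(both).

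| Correlation | Both | Either | Gap (points) |
|---|---|---|---|
| 0.3 | 47.7% | 84.3% | 36.5 |
| 0.7 | 54.4% | 77.6% | 23.1 |

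If 20% to 40% of children are dual and the others recover at 66%, overall recovery differs between the two readings by 0.20·23.1 = 4.6 to 0.40·36.5 = 14.6 points. Power for a 15-point difference at 135 per arm then runs from 77% (both) to 84% (either) at a 20% share, and from 74% to 88% at 40%, taking the wider gap.

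**4. Ignoring admission type (illustration).** Assume a half-and-half WHZ/MUAC mix and 135 per arm.

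- SD of the chance imbalance in mix: √(2·0.25/135) = 6.1 points
- Standard error of the unadjusted arm difference at 66%: √(2·0.66·0.34/135) = 5.8 points
- With recovery 55% in one type and 77% in the other, a 1-SD imbalance shifts the arm difference by 0.061·22 = 1.3 points
- Share of outcome variance explained by admission type, 0.25·g²/(0.66·0.34): 1.1% for g = 0.10, 4.5% for g = 0.20, 10.0% for g = 0.30

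**The case against.** **Pooling.** Under 1:1 randomization an arm-only model is valid. Chance imbalance in admission type is already inside the unadjusted standard error: 1.3 points against 5.8. This stands. A reader might infer that such imbalance biases the Aim 2 risk ratio, but nothing in the design supports that.

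**Size of the shift.** A reader might set the 5 to 15 points in step 3 against the 15-point design difference and conclude that interpretation alone could produce or erase the effect. The documents do not support this. The shift is in the overall recovery level, and the design figure is a difference between arms. Section 2.3 masks outcome assessors, so inconsistent reading should fall on both arms alike. The dual share, the correlation and the 66% margins in dual children are all assumed. The upper figure also supposes a wholesale switch from both to either.

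**Admission type is already fixed.** Baseline anthropometry precedes opening of the envelope, so admission type can be derived from pre-allocation data. This stands. What remains open is the recovery rule for dual-criterion children.

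**The rule may exist elsewhere.** The revision history says the definition was changed to fit the national program, and the study forms and standard medical protocol are listed as appendices. If one of them settles the dual case, Section 2.5 need only cite it.

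**Standing of the endpoint.** Recovery is a secondary outcome in a pilot. That limits the weight of the point, but Aim 2 is a named specific aim with its own power calculation.

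**Conclusion.** On the text supplied, the recovery endpoint is undefined for children who meet both entry criteria. The conflict between the inclusion and exclusion lists leaves it unclear whether that is some children or all of them. Because recovery ends weekly measurement, the choice has to be made prospectively. This is the stronger half of the point. It makes scoring inconsistent and the recovery level hard to interpret; it does not show an error favoring one arm.

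The absence of admission type from the Aim 2 model and the log-rank test is a cheap improvement forgone. Under assumed gaps of 10 to 30 points and an even mix, adjustment removes about 1% to 10% of outcome variance. That would take the 5.8-point standard error to about 5.7 (5.77·√0.989) or 5.5 (5.77·√0.900). The documents give no recovery rate by admission type, so this range rests on assumption.

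**What to change.** 1. Reconcile the inclusion and exclusion lines in Section 2.2 so that it is clear whether one criterion suffices for entry.
2. Derive admission type (WHZ only, MUAC only, both) from baseline measurements taken before the envelope is opened.
3. State in Section 2.5 one prespecified endpoint rule for dual-criterion children. The investigators choose it and reconcile it with the programme's discharge rule. If an appendix already contains the rule, cite it.
4. Derive the Aim 2 endpoint, time to recovery and nonresponse centrally from the recorded WHZ, MUAC, edema and complication data.
5. Report the alternative reading as a sensitivity analysis only where the measurements exist. Once weekly visits stop, they may not.
6. Add admission type as a covariate in the Aim 2 model, keeping the stated modified Poisson fallback, and stratify the time-to-recovery log-rank test by it.

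The cost is protocol and SAP wording plus one derived baseline variable. The Aim 2 model gains two parameters, and the log-binomial fit may fail to converge more often and need its fallback. The sample size does not change.

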## 2.6. Participant Timeline

**Figure 1.** Participant Timeline and Flow

- |  |
|--|
| 

• Malaria (RDT)

• Rectal swab (random subset of children)

• Hemoglobin

• Clinical examination outcomes (diagnoses, treatments)

 |
|--|

## 2.7. Study Team, Roles, Responsibilities

- **Investigators (UCSF).** The UCSF investigators will be responsible for the overall study design and implementation, data management and monitoring, data analysis, and dissemination of results in collaboration with UCSF investigators. The UCSF investigators will design and implement trainings for study procedures and maintain weekly communication with local Burkina Faso study staff.
- **Investigators (CRSN).** The CRSN investigators will be responsible for overall study design, implementation, data management and monitoring, data analysis, and dissemination of results in collaboration with UCSF investigators. The Burkina Faso investigators will oversee all local study activities, including training and regular supervision and monitoring of local study staff.
- **Medical Monitor.** The Medical Monitor will provide clinical oversight for the enrolled children. Study Team Members will report serious adverse events to the Medical Monitor within 24 hours of occurrence, and the Medical Monitor will determine whether or not the event is likely to be related to the study drug. In addition, the Medical Monitor will provide clinical guidance for the adverse event as needed. The Medical Monitor will participate on the Data and Safety Monitoring Committee.
- **Data and Safety Monitoring Committee.** The Data and Safety Monitoring Committee will provide independent oversight of data quality and patient safety during the course of the trial. See Section 8 for details.
- **Study Team Members (CRSN).** Study Team Members at CRSN will be responsible for implementation of all study procedures as described in Section 3, including recruitment, consent, enrollment and randomization, drug administration, and collection of all study data, including anthropometric and malaria assessments.
  - **CSPS Nurse.** A nurse at each CSPS will be trained to determine the randomization allocation of enrolled children by opening the envelopes and to administer azithromycin if indicated.
  - **Outcome Assessor.** One outcome assessor for each site will be trained to manage consent, enrollment, and collection of all study data, including outcome assessments.

### 3. PROCEDURES

#### 3.1. Training

All study personnel participating in study procedures (including enrollment and baseline assessment, randomization, drug administration, outcome assessments, and data collection) will participate in a 2-day initial training. Training will include a mix of lecture and practice. Participants must achieve a score of >80% on the training quiz in order to participate in the study and demonstrate agreement with a gold standard grader for all anthropometric assessments. Study personnel will be overseen by study investigators during the first week of enrollment, and refresher training will be conducted once a month during the course of the study.

#### 3.2. Anthropometry

Anthropometric assessments (height or length, weight, and MUAC) will be recorded by study personnel at baseline, weekly until recovery, and at week 8.

##### Supplies

- Mobile data collection device & accessories
- ShorrBoard
- Seca scale
- MUAC strips
- Chucks and alcohol swabs
- Pens and sharpie markers
- Trash bags
- Extra set of AA batteries (6)

##### Anthropometry Team

Two study team members will conduct anthropometry: 1) examiner and 2) recorder. The examiner will conduct the anthropometric assessments, and the recorder will enter data into the mobile application.

##### Measuring Length and Height

A lightweight measuring board will be used to measure the participant's height to the nearest 0.1 cm. Height and length will be assessed with a ShorrBoard. Depending on a child's age and ability to stand, measure the child's length or height.

- **Length:** If a child is less than 2 years old, or cannot stand alone, measure recumbent length. The recorder will select **Length** in the application to indicate that length was measured. A child's length is measured lying down (recumbent).
- **Height:** If a child is able to stand, measure standing height. The recorder will select **Height** in the application to indicate that height was measured. Height is measured standing upright.

If the child has braids or hair ornaments that will interfere with length/height measurements, remove them if possible. Check that any sandals, shoes, or socks have also been removed. Whether measuring length or height, the mother/guardian is needed to help with measurements and to soothe and comfort the child. Explain to the mother the reasons for the measurements, and describe the steps in the procedure. Answer any questions she might have. Show her and

tell her how she can help you. Explain that it is important to keep the child still and calm to obtain the best measurement.

#### **ShorrBoard Set-Up**

[figure not shown]
- 1) Remove ShorrBoard from bag.
- 2) Stand the ShorrBoard upright. You can step on the base of the board to keep it stable.
- 3) As you face the board, turn the non-removable bolt counterclockwise to release the extension piece. Note: the bolt remains attached to the back of the extension piece – do NOT remove it.
- 4) Slide the extension piece into the top end of the main board and fasten the clasp on the back of the board. Make sure the clasp is fastened properly.
- 5) The auto-lock sliding head/footpiece is stored in the base of the main board and can be moved up and down the length of the measuring board. It should stay in place on its own wherever you position it.
- 6) The measuring board must be placed against a firm surface for standing height (e.g. wall, table, tree, against a vehicle, etc.). Make sure the board is stable. If necessary, place items such as small rocks underneath the height board to stabilize it during the measurement.
- 7) Clean the equipment with alcohol swabs at the beginning of each day, and clean with alcohol swabs between each participant.

*Note:* when you set up the board each day, examine each of the pieces to check for damage.

#### **Measure Length**

1. Cover the length board with a chuck for hygiene and for the baby's comfort.
2. We usually have the assistant anthropometrist hold the baby's head and the lead anthropometrist manage the legs and feet. The mother stands to the side and focuses primarily on soothing the baby. The lead anthropometrist calls out the measurement and the assistant repeats it and then records it on the tablet.
3. Ask the mother to stand nearby and focus on soothing the baby.
4. The assistant anthropometrist will place the baby on the length board on his/her back with his/her head fixed against the headboard, compressing the hair and will hold the baby's head in place while the measurement is taken. The assistant should move quickly and surely without distressing the baby.
5. The assistant anthropometrist will quickly position the head so that an imaginary vertical line from the ear canal to the lower border of the eye socket is perpendicular to the board. (The child's eyes should be looking straight up.)
6. **Speed is important.** The lead anthropometrist will manage the baby's legs and feet. Standing on the side of the length board where you can see the measuring tape and move the footboard:
  - a. Check that the child lies straight along the board and does not change position.
  - b. Shoulders should touch the board, and the spine should not be arched. Ask the mother to inform you if the child arches the back or moves out of position.
  - c. Hold down the child's legs with the one hand and move the footboard with the other. Apply gentle pressure to the knees to straighten the legs as far as they can go without causing injury or distress. **Note: it is not possible to straighten the knees of newborns to the same degree as older children. Their knees are fragile and could be easily injured, so apply only gentle pressure.**

[figure not shown]
- d. If a child is extremely agitated and both legs cannot be held in position, measure with one leg in position.
  - e. While holding the knees, pull the footboard against the child's feet. Many babies will point their toes, but the lead anthropometrist should ensure the feet are perpendicular to the back of the board as much as possible.
7. **Upon reading the measurement, the examiner will clearly call out the number to the recorder.** Record the child's length in centimeters to the last completed 0.1 cm. (1.0 mm).
  8. Keeping the child in place, release the sliding footboard, and prepare to repeat the measurement. Re-position the child for a second and third measurement.

